9.7.2.4. Case Validation/Adjudication via Medical Records Review

Diagnostic validation of identified atrial fibrillation cases among individuals administered ABRYSVO will be conducted in a randomly selected representative sample of up to 100 cases per interim/final report, as available and feasible.

An adjudication charter will be developed to govern medical records review and case validation/adjudication. Specifically, validation of atrial fibrillation cases will be performed through patient medical chart review in collaboration with an adjudication committee consisting of trained healthcare professionals.⁷⁰ Further details will be described in the SAP.

Positive predictive value (PPV) will be calculated based on adjudication results as the proportion of atrial fibrillation cases deemed as true cases among the total number of adjudicated cases. Generally, PPV of 70% or greater is considered as sufficiently high.⁷¹ To be conservative, if the lower bound of the 95% CI of the PPV is less than 70% at the interim analysis, the algorithm used to identify incident atrial fibrillation using codified data may be updated in subsequent analyses and atrial fibrillation cases identified with the new algorithm will be re-adjudicated. If the lower bound of the 95% CI for PPV is equal to or greater than 70% in the interim report, chart adjudication may be waived for the final report.

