9.1.1. Primary Design - Internal Comparator Cohort Design (Contemporary Control Design)

To examine atrial fibrillation and supraventricular arrhythmia following ABRYSVO vaccination, days 0-3 will be used to define the risk interval, comprising a length of 4 days (ie, from the day of vaccination through the 3 days that follow, as only the date and not exact timing of vaccination will be known) for the primary analysis. This risk interval was selected based on post-marketing reports indicating atrial fibrillation onset less than one day after ABRYSVO administration, while accounting for a potential delay between the actual event

onset and when individuals seek care. As secondary analyses, days 0-1 comprising a length of 2 days (ie, the day of vaccination and the day following) will be used to define the risk interval, and days 0-30 comprising a length of 31 days (ie, the date of vaccination through the 30 days that follow) will be used to define the risk interval, similar to other studies that evaluated the risk for cardiac events (eg, myocarditis and pericarditis) to assess the safety profile of COVID-19 vaccines. ¹⁰⁻¹⁴ To reduce outcome misclassification, a confirmed case will require a diagnosis of atrial fibrillation (or supraventricular arrythmia) in the risk interval, with a confirmatory diagnosis within the subsequent 30 days for the primary and secondary analyses with different risk interval lengths (see Section 9.3.2).^{8,9}

Multivariable adjusted analyses will be performed comparing individuals who received ABRYSVO to individuals who received another vaccine (eg, influenza vaccine, COVID-19 vaccine, and other pre-specified vaccines such as shingles, hepatitis B listed in Section 9.3.3) at that point in time (+/- 30 days) [ie, contemporary vaccinated controls] in the primary analysis. The ABRYSVO cohort's index date will be defined as the date of vaccination with ABRYSVO. The vaccinated controls' index date will be defined as the date on which the individual received another vaccine that is within 30 days of a corresponding ABRYSVO vaccinee's vaccination date; these individuals can later receive ABRYSVO and enter the vaccination group if all eligibility criteria are met.

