9.1.3. Medical Records Review

Cases of atrial fibrillation among individuals vaccinated with ABRYSVO will be validated/adjudicated (see Section 9.7.2.4 Case Validation/Adjudication via Medical Records Review for further details). VA analysts will produce a line listing of cases for medical records data abstraction. The listing will contain an identifier and other relevant information

that is sufficient to identify the correct EHR for each patient (detailed in Section 9.6.1 "Case Report Forms (CRF)"). The listing will also include sex, date of birth, date of vaccination with ABRYSVO, date of atrial fibrillation diagnosis, age at diagnosis of atrial fibrillation, days lapsed since vaccination, and co-administered vaccines.

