9.2.2. Exclusion Criteria

Individuals meeting any of the following criteria will be excluded from the study:

- Individuals with a record for atrial fibrillation or other supraventricular arrhythmia during the baseline period
- Individuals with missing date of birth

For the analyses using the SCRI design, a subset of eligible individuals from the ABRYSVO cohort that experienced atrial fibrillation or other supraventricular arrhythmia in the risk or control intervals will be included.

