9.3.2. Outcomes

The study's primary outcome, new onset atrial fibrillation, will be identified by a diagnosis code for atrial fibrillation in any setting during the 0-3 day risk interval (or 0-1 day or 0-30 day risk interval for secondary analysis), or corresponding control interval, followed by a confirmatory diagnosis within 30 days after the initial diagnosis. To be considered an incident case, no diagnosis for atrial fibrillation or other supraventricular arrhythmia should be observed in the 2 years prior to the index date (ie, "clean window," the occurrence-free

baseline period used to define incident outcomes during which individuals enter the study cohort only if the safety event did not occur during this period).^{8,9}

The secondary outcome of the study will be new onset supraventricular arrhythmia, including atrial fibrillation, and will be identified in the same manner as the primary outcome (ie, a diagnosis code for the event in any setting during the risk interval, or control interval, followed by a confirmatory diagnosis within 30 days after the initial diagnosis, and no diagnosis code for atrial fibrillation or other supraventricular arrhythmia in the 2-year clean window).

The study outcomes and operational definitions of the outcome variables based on International Classification of Diseases, Tenth Revision, Clinical Modification (ICD-10-CM) diagnosis codes are outlined in Table 1. ICD-10-CM diagnosis codes occurring in any position (ie, primary or secondary) in OP (including emergency department [ED]) and/or IP settings will be used to identify safety events.

Table 1. Safety events, including outcome algorithms and risk and control intervals

Safety Event	Operational Definition Defined by the presence of any of the following ICD- 10-CM codes (inclusive):	Setting (IP, OP)	Clean Window	Risk Interval (Days)	Post- Vaccination Control Interval for SCRI Design (Days)
Atrial fibrillation (primary outcome) ⁵⁰	 I48.0, Paroxysmal atrial fibrillation I48.19, Other persistent atrial fibrillation I48.20, Chronic atrial fibrillation, unspecified I48.91, Unspecified atrial fibrillation 	IP or OP	2 years	Primary: 0-3 Secondary : 0-1 and 0-30	Primary: 4-10 Secondary: 2-8 and 31- 61

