9.7.2.2. Comparison with Contemporary Controls

Average treatment effect among the treated (ATT) weighting will be used to ensure baseline comparability between the ABRYSVO vaccinated cohort vs. contemporary vaccinated control cohort and between the ABRYSVO vaccinated cohort vs. contemporary unvaccinated control cohort. ATT weighting creates a "pseudo-population" in which the distribution of covariates is, on average, the same in each cohort. ⁶⁸ Specifically, ATT weights will be calculated to allow for estimation of the average treatment effect among individuals receiving ABRYSVO.⁶⁹ This approach will be taken to ensure that inference from the analysis will be applicable to this population. Individuals receiving ABRYSVO will receive an ATT weight of one. Individuals not receiving ABRYSVO will receive an ATT weight equal to the odds of receiving ABRYSVO conditional on their demographic and clinical characteristics as of the index date, which will be calculated based on the propensity score (PS). The PS is defined as an individual's probability of receiving ABRYSVO, conditional on observed baseline covariates, and will be calculated using a logistic regression model. The logistic regression model will include the cohort variable (ie, ABRYSVO vs. vaccinated or unvaccinated control) as the dependent variable, and the independent variables will include variables deemed clinically important and baseline covariates that have standardized differences ≥10% between the two cohorts. Specifically, ATT weights will be PS/(1-PS) for individuals with no record of ABRYSVO. The distribution of weights will be examined to assess extreme values, and truncation will be considered if necessary.

Weighted Cox regression with robust standard errors to account for within-subject correlation will be conducted to compare the risk of safety events between cohorts. Hazard ratios and corresponding 95% CIs will be summarized.

9.7.2.3. SCRI Design using the Conditional Poisson Regression for Comparison to Post-vaccination Control Intervals

SCRI design with post-vaccination control time period will include cases (ie, individuals vaccinated with ABRYSVO who experience safety events following vaccination) who have at least 41 days (or 38 days or 91 days for secondary analysis) of enrollment post-index to compare the incidence of safety events occurring in the risk interval following vaccination with the incidence of safety events occurring during the post-vaccination control interval.

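### Secondary SCRI design, low-cost improvement: the final chart review may be waived on one pooled PPV, which does not by itself show whether false or pre-vaccination AF is concentrated on day 0

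*Protocol*

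**What the plan says.** Protocol Section 9.7.2.4 has coded AF cases in ABRYSVO recipients checked against charts. The review "will be conducted in a randomly selected representative sample of up to 100 cases per interim/final report". The summary measure is a single proportion: "Positive predictive value (PPV) will be calculated based on adjudication results as the proportion of atrial fibrillation cases deemed as true cases", with all adjudicated cases as the denominator. If the lower 95% limit is below 70% at the interim, the algorithm may be changed and cases re-adjudicated. If it is 70% or more, "chart adjudication may be waived for the final report". The same section leaves the conduct of adjudication to a charter and further detail to the SAP.

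The SCRI in Section 9.7.2.3 uses cases, that is "individuals vaccinated with ABRYSVO who experience safety events following vaccination", and compares days 0-3 with days 4-10. Four other provisions bear on it:

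- Section 9.1.1 includes day 0 in the risk interval, "as only the date and not exact timing of vaccination will be known", and dates onset by the first case record.
- Section 9.2.2 excludes "Individuals with a record for atrial fibrillation or other supraventricular arrhythmia during the baseline period", which is two years of recorded diagnoses. Section 9.4 says that care outside VHA facilities is not in the main data source.
- Section 9.3.2 requires the first code to be "followed by a confirmatory diagnosis within 30 days after the initial diagnosis".
- Section 9.1.3 puts on the case listing "date of atrial fibrillation diagnosis, age at diagnosis of atrial fibrillation, days lapsed since vaccination, and co-administered vaccines".

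**The concern.** The SCRI contrasts two short intervals in the same people. Its bias from miscoding depends on how the PPV differs between those intervals, not on the PPV averaged over them. The protocol's own rules leave a route to a difference. AF last recorded more than two years ago, AF diagnosed outside VHA, or AF already present at the visit can first be coded on the vaccination day, which falls in the risk interval. Days 4-10 contain no scheduled vaccination visit. The confirmatory code removes rule-out diagnoses, but real pre-existing AF will usually be coded again and so passes.

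The waiver criterion is written into the protocol and looks only at the pooled figure. It could be met while the SCRI ratio is too high, and the charts that would explain the excess could then be skipped for the final report. At stake is a false or unexplained SCRI signal in a study that is a post-marketing commitment.

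**Working it through.** **Inputs from the Protocol.** Background rate 33.9 per 1,000 person-years and 38,453 vaccinees for a ratio of 2 (Section 9.5.1, Table 3, age 60 and older); risk interval 4 days, control interval 7 days (Sections 9.1.1 and 9.1.2); up to 100 charts; lower 95% limit of at least 70%. **Assumed, because the documents give no value:** the share f of day 0-10 cases that are earlier AF coded on day 0; the accuracy of the other codes; an exact (Clopper-Pearson) limit; a chart sample drawn from days 0-10.

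**1. The plan's own figure.** Table 3 needs 25 control-interval events for a ratio of 2: 25 / (0.0339 × 7/365) = 38,453. This reproduces with a 4-day risk interval and 53 events in all. With no vaccine effect, the same cohort gives about 14.3 cases in days 0-3, 25.0 in days 4-10 and 39.3 in days 0-10.

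**2. What the gate tolerates.** With 100 charts, 80 true cases give a lower limit of 70.8% and 79 give 69.7%, so up to 20 false cases pass. Nothing limits which days they fall on.

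**3. Effect on the SCRI when the true ratio is 1.** True cases split 4:7 and the share f is added to day 0:

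apparent ratio = [(1−f)·4/11 + f] / [(1−f)·7/11] × 7/4

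At f = 10%: (0.4273 / 0.5727) × 1.75 = 1.31.

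**4. Does the gate pass?** If adjudicators count earlier AF as false, the expected PPV is accuracy × (1−f), and the gate passes when at least 80 of 100 are true (binomial):

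| Share f | Apparent ratio | PPV at 95% accuracy | Gate passes, 95% accuracy | Gate passes, 90% accuracy |
|---|---|---|---|---|
| 5% | 1.14 | 90.3% | >99% | 95% |
| 10% | 1.31 | 85.5% | 95% | 66% |
| 15% | 1.49 | 80.8% | 63% | 24% |
| 20% | 1.69 | 76.0% | 21% | 4% |

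If adjudicators instead count earlier AF as true AF, the PPV does not respond to f. At 90% accuracy the gate then passes more than 99% of the time at every f in the table.

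**5. Effect on the test.** With an exact one-sided 5% test at Table 3's 53 events, the false-signal rate is 4% at f = 0, 10% at f = 5% and 21% at f = 10%. At the 156 events planned for a ratio of 1.5, it is 4%, 17% and 44%.

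**6. Dependence on the sampling frame.** Add 6 earlier cases on day 0 to the 39 expected in days 0-10. The apparent ratio is ((14.3+6)/4) / (25.0/7) = 1.42.

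- Charts from days 0-10, all other codes correct: 39/45 true, lower limit 73%. The gate passes.
- Same frame, about 90% of the other 39 correct: 35/45, lower limit 63%. The gate fails.
- Charts from days 0-3 only: 14/20, lower limit 46%. The gate clearly fails.
- Charts from days 0-30: about 111 background cases, so a random 100 holds about 100 × 4/31 = 13 from days 0-3 before any extra cases. The day-0 excess is diluted.

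**The case against.** The strongest reply is that much of this is charter or SAP content. Section 9.7.2.4 defers to both, and onset categories, sampling strata and extra sensitivity analyses may be set there. That is right, and their absence from the protocol is no fault. What the protocol does fix is the waiver criterion, and that names only the overall PPV.

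A reader might infer that the pooled PPV cannot reveal pre-vaccination AF at all. The documents do not support this. The outcome is new-onset AF, and the algorithm is described as identifying incident AF, so a charter could well count earlier AF as false. It would then lower the PPV, and a large share would usually fail the gate. A days 0-3 sampling frame, or ordinary coding error elsewhere, would also make the gate stricter.

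The waiver is optional and follows an interim review whose listing already carries days since vaccination. The study team could therefore notice clustering on day 0; the criterion does not ask them to look. Other safeguards help in part. Section 9.7.2.5 describes the AF history of cases, but not whether onset preceded the injection. The negative control outcomes in Section 9.7.4.1 may reveal visit-day coding in general, but not its size for AF.

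A reader might also extend the point to the primary cohort comparison. Vaccinated controls have a vaccination on their own day 0, and unvaccinated controls have an encounter-based index date where the matched vaccination involved an encounter (Section 9.2.1). Visit-day coding is therefore partly matched there, and the point is limited to the SCRI.

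**Conclusion.** The point holds as a minor to moderate improvement to the secondary SCRI design. The waiver criterion is a pooled PPV, and that figure does not by itself show whether false or pre-vaccination AF is concentrated on day 0. The gate is most likely to pass with a biased ratio at day-0 shares of about 5-10%, where a true ratio of 1 reads 1.14 to 1.31. By a 20% share it usually fails, provided that earlier AF is counted as false. These results rest on assumed shares, assumed coding accuracy and a days 0-10 frame. They show what the rule allows, not how often it would happen. No stated figure in the plan is wrong on this point.

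**What to change.** Amend Section 9.7.2.4 and the adjudication charter, keeping the coded analyses as planned and the limit of 100 charts:

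1. Adjudicate each reviewed case as AF onset before or after vaccination.
2. Sample by interval (days 0-3, days 4-10, later) with known fractions, and weight back for the overall PPV.
3. Report PPV by interval with its confidence interval, without a pass/fail test between intervals.
4. Permit the final-report waiver only after these interval results have been reported and considered, not on the pooled PPV alone.
5. Optionally, where all day 0-10 cases are reviewed, add a sensitivity SCRI restricted to chart-confirmed new-onset cases.

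**Cost.** A few lines of text; days since vaccination is already on the listing. At a ratio of 2 and 38,453 vaccinees, all 53 day 0-10 cases plus 47 later ones fit within 100 charts. At 156 events they do not, so those strata would be sampled and item 5 would drop out.

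At a PPV of 0.8, the standard error of the overall PPV rises from √(0.8 × 0.2/100) = 0.040 to 0.041 if the frame is days 0-30, or 0.047 if it is days 0-61. Interval PPVs will be imprecise: 40 true of 50 gives 66% to 90%. Some final charts that might have been waived may have to be read.

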9.7.2.5. Analysis of Risk Factors for Atrial Fibrillation

If an increased risk of atrial fibrillation following ABRYSVO vaccination is observed from the analyses described above, a risk factor analysis will be conducted via logistic regression among individuals vaccinated with ABRYSVO. Specifically, up to ten baseline characteristics will be selected a priori (eg, age, sex, race/ethnicity, history of atrial fibrillation prior to baseline period, co-administration of influenza vaccine, COVID-19 vaccine, or other pre-specified vaccines such as shingles, hepatitis B] listed in Section 9.3.3) and included in a multivariable logistic regression model with atrial fibrillation as the outcome to determine if any of the select baseline characteristics may be risk factors associated with atrial fibrillation.

Co-administration with other vaccines and patient characteristics during the two-year baseline period (or based on all available data for history of atrial fibrillation) will also be

described to enhance understanding of the healthcare profiles of atrial fibrillation cases. Co-administration will be defined as receipt of ABRYSVO and another vaccine (ie, influenza vaccine, COVID-19 vaccine, or other pre-specified vaccines [eg, shingles, hepatitis B] listed in Section 9.3.3) on the same day.¹⁸

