9.2.1. Inclusion Criteria

Three cohorts will be defined for the main analyses.

- A. A cohort of individuals who received ABRYSVO will form the ABRYSVO cohort and must have:
 - A record for at least one dose of ABRYSVO in the study period from 31 May 2023 (or earliest date of vaccine availability for the indicated population) to 31 May 2026; the date of ABRYSVO vaccination will define the index date for this cohort
 - o No record of an RSV vaccine from a manufacturer other than Pfizer
- B. A cohort of individuals who did not receive ABRYSVO but received another vaccine will form the contemporary vaccinated control cohort and must have:
 - A record for another vaccine (eg, influenza vaccine, COVID-19 vaccine, and other pre-specified vaccines such as shingles, hepatitis B listed in Section 9.3.3) within 30 days of a corresponding ABRYSVO vaccinee's vaccination date; the control's index date will be the date of the control's non-RSV vaccine
 - No record for any RSV vaccine on the index date or in the baseline period (ie, 2 years prior to the index date)
 - Individuals in the vaccinated control cohort who go on to receive an RSV vaccine following their index date will be censored at the time of RSV vaccination. If the RSV vaccine is ABRYSVO, these individuals will contribute to the ABRYSVO cohort starting from the date of ABRYSVO receipt.
- C. A cohort of individuals who did not receive ABRYSVO or another vaccine on the index date but had at least one vaccination record in the year prior to the index date will form the contemporary unvaccinated control cohort and must have:
 - No record for any RSV vaccine on or within 30 days of the index date or in the baseline period (ie, 2 years prior to the index date)

- No record for any other vaccine (eg, those listed in Section 9.3.3) on or within 30 days of the index date
 - This cohort will be assigned an index date matched to a corresponding ABRYSVO vaccinee's vaccination date. If the vaccination is associated with a healthcare encounter (ie, inpatient [IP] or outpatient [OP] visit), the unvaccinated control will be required to have a healthcare encounter within 30 days of the assigned index date, and the date of the healthcare encounter will be set as the index date for the unvaccinated control.

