9.2.3. Subgroups

Safety surveillance may be conducted for subgroups of interest as applicable to each age group, including, but not limited to the ones described below.

The following subgroups will be analyzed for the 18-59 years old age group and the 60 years and older age group:

- Individuals in VA priority group 1; These individuals have either the highest levels of service connected disability (≥50% disabling), are considered unemployable, or have received the medal of honor. Individuals categorized as priority group 1 are the highest priority for VHA care. This will ensure that the individual is more likely to receive all of their care from a VA facility;
- Females enrolled in the VHA (pending sufficient sample size);

• Individuals with co-administration with other vaccines (ie, influenza vaccine, COVID-19 vaccine, or other pre-specified vaccines [eg, shingles, hepatitis B] listed in Section 9.3.3) on the same day.¹⁸

The following subgroups will be analyzed for the 60 years and older age group only:

- Individuals with specific conditions that increase the risk for severe RSV as defined by the CDC during the baseline period; list of conditions may be updated to align with the most current CDC definition at the time of data analysis (see Section 9.2.1);
- Different age groups defined by age on the index date, eg, 60 to 69 years, 70 to 79 years, ≥80 years;
- Individuals enrolled in the VHA with dual coverage who are also identified in the Centers for Medicare & Medicaid Services (CMS) Medicare administrative claims data, which will be linked to the Corporate Data Warehouse (CDW) to supplement the data for a more complete evaluation of healthcare encounters.

Additional subgroups of interest may be assessed as additional information becomes available from ongoing clinical trials, Vaccine Adverse Event Reporting System (VAERS), and other sources that will inform the ABRYSVO safety profile.

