9.7.3. Subgroup Analysis

Separate analyses of baseline characteristics and safety analyses in subgroups of interest may be conducted based on feasibility, sample size, and data availability. These analyses will be performed for all subgroups listed in Section 9.2.3 as applicable to each age group. For each subgroup, a new set of ATT weights will be generated in the comparison with contemporary vaccinated and unvaccinated controls, and analyses will be conducted as described above.

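### The subgroup template in Section 9.7.3 does not fit the co-administration subgroup: it leaves either no matching controls or a hazard ratio that mixes the co-vaccine's effect with that of ABRYSVO

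*Protocol*

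**What the plan says.** Section 9.2.3 lists, for both age groups, the subgroup "Individuals with co-administration with other vaccines (ie, influenza vaccine", COVID-19 vaccine or another pre-specified vaccine, given on the same day. That line does not name ABRYSVO. Section 9.7.2.5, on the risk-factor analysis, does: "Co-administration will be defined as receipt of ABRYSVO and another vaccine" on the same day.

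Section 9.7.3 makes subgroup analyses conditional on feasibility, sample size and data, and then states: "These analyses will be performed for all subgroups listed in Section 9.2.3 as applicable to each age group". It adds: "For each subgroup, a new set of ATT weights will be generated in the comparison with contemporary vaccinated and unvaccinated controls". It does not say whether a control must itself meet the subgroup definition.

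Section 9.2.1 sets the control cohorts. Cohort B must have "No record for any RSV vaccine on the index date or in the baseline period (ie, 2 years prior to the index date"). Cohort C must have "No record for any RSV vaccine on or within 30 days of the index date or in the baseline period", and also "No record for any other vaccine (eg, those listed in Section 9.3.3) on or within 30 days of the index date".

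Section 8 makes it a secondary objective to assess whether this sub-cohort has an increased risk of atrial fibrillation and supraventricular arrhythmia after ABRYSVO.

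**The concern.** The other subgroups (age band, sex, priority group, CDC risk condition, Medicare linkage) are traits that a control can share. Restricting both arms to women, for example, leaves women in every cohort. Co-administration is different because it describes the exposure itself, so a template built for baseline traits does not carry over to it.

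What is at stake is the comparative answer to a listed secondary objective. Section 9.9 reads the contemporary-control comparison as the increase in risk due to ABRYSVO. In this subgroup, an elevated ratio could come from the co-vaccine, and a co-vaccine associated with fewer recorded events could hide an elevation caused by ABRYSVO.

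**Working it through.** The check is one of membership; the protocol gives no figure to reproduce. The inputs are the cohort rules in Section 9.2.1, the subgroup line in 9.2.3 and the definition in 9.7.2.5.

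| Person | ABRYSVO at index | Other vaccine at index | Member under 9.7.2.5 | Member under 9.2.3 wording alone |
|---|---|---|---|---|
| Cohort A, with same-day co-vaccine | yes | yes | yes | yes |
| Cohort A, ABRYSVO only | yes | no | no | no |
| Cohort B, one non-RSV vaccine | no | yes | no | no |
| Cohort B, two or more non-RSV vaccines that day | no | yes | no | possibly |
| Cohort C | no | no | no | no |

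**Reading 1: both arms must meet the definition.** Cohort C supplies 0 controls on either wording. Cohort B supplies 0 under 9.7.2.5. On the 9.2.3 wording alone, it supplies at most those given two or more non-RSV vaccines on one day. Where there are no controls, the propensity score, the ATT weights and the hazard ratio are all undefined.

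**Reading 2: only the ABRYSVO arm is restricted.** A ratio can be computed. Suppose ABRYSVO has no effect and co-vaccine X multiplies the event rate in the risk interval by R.

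- Against cohort C, every exposed person has a co-vaccine and no control does. If all receive X, the ratio equals R. Covariate weighting cannot remove this, because nobody in cohort C has a same-day vaccine to be weighted up.
- Against cohort B, let a share a of the exposed and a share b of the controls receive X, let the remaining vaccines have no effect, and let the weights not balance vaccine type. The ratio is (aR + 1 − a) / (bR + 1 − b), which equals 1 only if a = b or R = 1.

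The protocol gives no value for R, a or b. The following values are assumptions, chosen only to show how the formulas behave, with a = 0.6 and b = 0.3:

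| Assumed R | Ratio against C | Ratio against B |
|---|---|---|
| 1.1 | 1.1 | 1.06 / 1.03 = 1.03 |
| 1.3 | 1.3 | 1.18 / 1.09 = 1.08 |
| 1.5 | 1.5 | 1.30 / 1.15 = 1.13 |

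With R below 1, both ratios fall below 1.

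**Analyses without controls.** Incidence rates and the SCRI analysis can still be run in this subgroup. A co-vaccine given on the same day shares day 0 with ABRYSVO, however, so the SCRI ratio of days 0-3 to days 4-10 also reflects both products together.

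**The case against.** A reader might infer that the subgroup hazard ratios cannot be formed at all and that both control cohorts are necessarily empty. The protocol does not support that. Section 9.7.3 never requires controls to meet the subgroup definition, and the objectives describe sub-cohorts followed after ABRYSVO, which fits restricting the exposed arm only. The 9.7.2.5 definition sits in an analysis confined to ABRYSVO recipients, so naming the product there is natural. Section 9.7.3 points to 9.2.3, whose wording could admit cohort B members given two non-RSV vaccines together. The count of zero is therefore unconditional for cohort C only.

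Three further points have weight. First, Section 9.3.3 lists co-administered immunizations by type as a possible covariate; if a control's index vaccine were coded there, weighting could narrow the gap against cohort B. Second, ABRYSVO plus a co-vaccine against no vaccine is a legitimate joint-exposure contrast. Third, the analysis is secondary and optional, and Section 9.7 leaves detailed methods to the SAP.

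These points limit the finding without removing it. Coding the index vaccine cannot help against cohort C. A joint contrast is acceptable if it is called one, but Section 9.9 attributes the result to ABRYSVO. Being optional does not define a comparator if the analysis is run. Nor is this only detail left for the SAP: the protocol itself fixes the definition, the eligibility rules and the comparison, and for this subgroup they do not fit together.

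**Conclusion.** The point stands as a mismatch between the template and this one subgroup. No cohort C control can belong to it on any reading, and no cohort B control can under the 9.7.2.5 definition. If controls are left unrestricted, the hazard ratio exists but does not estimate the effect of ABRYSVO. Its distance from that effect depends on the co-vaccine's own association with the outcome and, for cohort B, on the vaccine mix in each arm and on what the weights balance. The protocol supplies none of these, so the size is unknown; the illustrative ratios are not estimates of it. The main analyses, the other subgroups and this subgroup's incidence rates are unaffected. The change is worth making before analysis because a secondary objective depends on it and the remedy is cheap.

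**What to change.** In Sections 9.2.3 and 9.7.3, give this subgroup its own comparison:

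- Compare recipients of ABRYSVO plus vaccine type X on the same day with cohort B controls whose index-date vaccine, or same-day set of vaccines, is X. Match exactly on vaccine type and apply ATT weights to the remaining covariates. The contrast is then ABRYSVO added to X.
- Drop the cohort C contrast for this subgroup, or label it explicitly as the joint effect of ABRYSVO plus co-vaccine against no vaccine.
- Label the subgroup's SCRI ratio as a joint effect as well.
- Use one definition of co-administration throughout. If it is the 9.7.2.5 definition, keep that indicator out of this subgroup's propensity model, because it would be constant within each arm.

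The cost is protocol or SAP wording and one matching variable built from immunization records already held. The downside is fewer controls for rare co-vaccines or combinations.
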